3.2.2 Secondary

- Assessment of immunogenicity by measurement of anti-NEOD001 antibodies
- Serum NEOD001 concentrations (sparse sampling) will be pooled with similar samples from other studies in a population PK analysis

3.2.3 Exploratory

- Time to all-cause mortality from baseline in Study NEOD001-001
- Change from baseline (of this study) in the 6MWT
- Change from baseline (of this study) in the SF-36

3.3 NUMBER OF SITES AND SUBJECTS

Multi-center study in approximately 70 subjects.

3.4 RANDOMIZATION AND BLINDING

Not applicable.

3.5 ESTIMATED STUDY AND TREATMENT DURATION

A subject's study duration may be up to 38 months or until the study is terminated (per Section 4.5), whichever occurs first. The study consists of a Screening Phase (1 month), Treatment Phase (36 months), and the End of Study (EOS) Visit 30 (\pm 5) days after the last dose.

3.6 DEFINITION OF END OF STUDY

The study is expected to be completed approximately 3 years after the last subject is enrolled. The study is considered completed with the last study visit for the last subject participating in the study or if the study is terminated, whichever occurs first, see Section 4.5.

4 SELECTION, DISCONTINUATION, AND WITHDRAWAL OF SUBJECTS

4.1 INCLUSION CRITERIA

Subject must meet *all* of the following:

1. Previously enrolled and treated for at least 9 months in Study NEOD001-001
2. Ability to understand and willingness to sign an informed consent form (ICF) prior to initiation of any study procedures
3. Has adequate bone marrow reserve, hepatic and renal function, as demonstrated by:
 - Absolute neutrophil count (ANC) $\geq 1.0 \times 10^9/L$
 - Platelet count $\geq 75 \times 10^9/L$
 - Hemoglobin ≥ 9 g/dL
 - Total bilirubin ≤ 2 times the upper limit of normal (\times ULN)
 - Aspartate aminotransferase (AST) and/or alanine aminotransferase (ALT) $\leq 3 \times$ ULN
 - Estimated glomerular filtration rate ≥ 30 mL/minute
4. Seated systolic blood pressure (BP) 90 to 180 mmHg
5. ECOG PS 0 to 2
6. Women of childbearing potential (WOCBP) must have a negative serum pregnancy test within 28 days prior to the first administration of study drug and agree to use highly effective physician-approved contraception ([Appendix 1](#)) from 30 days prior to the first study drug administration to 90 days following the last study drug administration
7. Male subjects must be surgically sterile or must agree to use highly effective physician-approved contraception ([Appendix 1](#)) from 30 days prior to the first study drug administration to 90 days following the last study drug administration

4.2 EXCLUSION CRITERIA

Subject must *not* meet any of the following:

1. Any new medical contraindication or clinically significant abnormality on physical, neurological, laboratory, vital signs, or ECG examination (e.g., atrial fibrillation; *with the exception* of subjects for whom the ventricular rate is controlled) that precludes continued or initiation of treatment with NEOD001 or participation in the study
2. History of Grade ≥ 3 infusion-associated adverse events (AEs) or hypersensitivities to NEOD001 or any of its excipients

3. Treatment with any anticancer therapy (standard or investigational) within the 14 days prior to the first dose of study drug. In addition, subjects must have fully recovered (i.e., National Cancer Institute Common Terminology Criteria for Adverse Events [CTCAE] Grade 1 [*exception*: subjects with prior bortezomib may have CTCAE Grade 2 neuropathy]) from the clinically significant toxic effects of that treatment
4. Received any of the following within the specified time frame prior to the first administration of study drug:
 - Hematopoietic growth factors, transfusions of blood or blood products within 1 week
 - Major surgery within 2 weeks
 - Radiotherapy within 2 weeks
 - Transplant within 8 weeks
 - Investigational drug other than NEOD001 within 4 weeks
 - Another experimental anti-amyloid therapy other than NEOD001 within 2 years
5. Uncontrolled symptomatic orthostatic hypotension
6. Myocardial infarction, uncontrolled angina, uncontrolled ventricular arrhythmias, or electrocardiographic evidence of acute ischemia, within 6 months prior to the first dose of study drug
7. Uncontrolled infection
8. Secondary malignancy, *with the exception of*:
 - Adequately treated basal cell carcinoma, squamous cell carcinoma, or in situ cervical cancer
 - Adequately treated stage I cancer from which the subject is currently in remission
 - Any other cancer from which the subject has been disease-free for ≥ 3 years
9. Uncontrolled human immunodeficiency virus (HIV), hepatitis B, or hepatitis C infection
10. Women who are lactating

4.3 EARLY TREATMENT DISCONTINUATION

If the subject discontinues study drug prior to completing 36 months of treatment, they should return for an EOS Visit 30 (\pm 5) days after their final administration of study drug as per Section 6.1.3. If a subject fails to return for the scheduled visit, a documented effort must be made to determine the reason. If the subject cannot be reached by telephone after 2 attempts, a certified letter will be sent to the subject (or the subject's legally authorized representative, if appropriate) requesting contact with the Investigator. This information will be recorded in the study records.

Reasons for early discontinuation from study drug treatment may include, but are not limited to:

- A suspected NEOD001-related immunologic reaction – collect additional serum samples, if possible, during the period following the treatment stoppage to allow for the determination of the persistence of anti-NEOD001 antibodies. Samples should be collected at the EOS Visit and 3 months after the EOS Visit, if the subject agrees to return to the clinic.
- Occurrence of an AE or clinically significant laboratory abnormality that, in the opinion of the Investigator, warrants the subject's permanent discontinuation from study drug treatment; the Medical Monitor should be notified as soon as possible of any discontinuation of study drug due to an AE.
- Suspected or confirmed pregnancy or nursing during study treatment period. Female subjects whose pregnancy test is positive at the EOS Visit must be followed to term or until termination of the pregnancy (Section 7.4.2).
- Subject requests to withdraw from the study treatment
- Subject requires or has taken medication prohibited by the protocol

4.4 EARLY TERMINATION FROM STUDY

Subject participation in this study will continue until EOS. Early termination occurs if the subject fails to complete the entire study, through the EOS Visit. Subjects may withdraw their consent to participate in this study at any time without prejudice. The Investigator must withdraw from the study any subject who requests to be withdrawn. A subject's participation in the study may be discontinued at any time at the discretion of the Investigator in accordance with his/her clinical judgment. The Sponsor or its designee should be notified in a timely manner of all subject discontinuations. When possible, the tests and evaluations listed for the EOS Visit should be carried out.

Early termination from the study may occur if:

- In the opinion of the Investigator, the subject cannot safely participate in the procedures required by the protocol
- Subject withdraws consent
- Subject is unwilling or unable to comply with the study requirements
- Subject is lost to follow-up

Vital status will be collected within legal and ethical boundaries for all randomized subjects receiving at least one dose of study drug and will be searched in public sources. During the study close-out period, survival status will be collected within legal and ethical boundaries for all randomized subjects who withdrew participation from the study. If vital status is determined, the subject will not be considered lost to follow-up.

4.5 TERMINATION OF THE CLINICAL STUDY, INVESTIGATOR, OR STUDY SITE

The Sponsor reserves the right to terminate the study, participation of an individual Investigator, or a study site at any time for any reason. Conditions that may warrant termination include, but are not limited to:

- Clinical or administrative reasons
- Discovery of an unexpected, relevant, or unacceptable risk to subjects
- Sponsor's discontinuation of further development of the study drug
- Study drug becomes commercially available
- Failure of the Investigator to comply with the protocol, the requirements of the Institutional Ethics Committee/Institutional Review Board (IEC/IRB) or Competent Authority, the Sponsor's procedures, or Good Clinical Practice (GCP) guidelines
- Inadequate recruitment of subjects by the Investigator

According to the study contract, the Investigator also reserves the right to terminate participation in the study.

4.6 REPLACEMENT OF SUBJECTS

As this is an open-label study for subjects previously enrolled and treated for at least 9 months in Study NEOD001-001, no subjects will be replaced.

5 TREATMENT OF SUBJECTS

5.1 STUDY THERAPY

5.1.1 Formulation, Packaging, and Labeling

The active study drug, NEOD001, is supplied as a sterile, lyophilized dosage form in a 20/25-mL vial containing 500 mg NEOD001. After reconstitution with 9.6 mL of sterile water for injection (WFI), the vial will contain 50 mg/mL of NEOD001, 25 mM L-Histidine, 230 mM Trehalose, and 0.02% Polysorbate 20. The labeling will comply with applicable regulatory requirements.

5.1.2 Shipping, Storage, and Handling

NEOD001 will be shipped to clinical sites in individual cartons (one vial per carton). Upon receipt, a study staff member will place the study drug in a refrigerator at a temperature ranging from 2°C to 8°C in a secure, locked location. Access to the study drug should be strictly limited to the study staff. Neither the Investigator nor any member of the study staff will distribute any of the study supplies to any person who is not participating in this study.

If a study staff member becomes aware that the study drug has not been properly handled (e.g., physical damage to carton/vial, temperature outside the 2°C to 8°C range in transit, or not stored at 2°C to 8°C in the clinic), follow the procedure outlined in the Pharmacy Manual or immediately contact the Study Monitor (contact information available in the Study Manual). In such an event, study drug should be quarantined in a 2°C to 8°C refrigerator and must not be administered to any subject until the drug has been approved for use.

It is expected that the site staff will maintain refrigerator temperature logs in the investigational product storage area, recording the temperature at least once each working day.

See Section 5.3 and the Pharmacy Manual for further details about shipping, storage and handling of NEOD001.

5.2 ACCOUNTABILITY AND RETURN OF STUDY SUPPLIES

The study drug will be dispensed at the discretion of the Investigator in accordance with the conditions specified in this protocol. It is the Investigator's responsibility to ensure that accurate records of study drug issuance and return are maintained.

All study drug provided by the Sponsor should be retained at the site until otherwise instructed in writing by the Sponsor. Upon completion of the study or termination of the investigational site, all unused vials of study drug supplied by the Sponsor can be destroyed locally as per local institutional guidelines and a copy of the destruction certificate supplied to the Sponsor or may be shipped to a depot designated by the Sponsor. Refer to the Pharmacy Manual for additional information.

5.3 DOSAGE, PREPARATION, AND ADMINISTRATION

Study drug consists of NEOD001. The NEOD001 dose is 24 mg/kg; however, the maximum dose administered is not to exceed 2500 mg. Therefore, subjects with a weight of 104.2 kg or greater will receive the maximum dose of 2500 mg. The subject's weight during Screening may be used for calculation of the first dose. Subsequent doses may be calculated based on the current weight at that visit or using the baseline weight, based on the site's institutional guidelines. A change of $\pm 10\%$ from the weight being used for dosing should trigger recalculation of the dose based on the new weight unless thought to be exclusively due to fluid fluctuation (e.g., edema).

Each vial of 500 mg of NEOD001 will be reconstituted with 9.6 mL sterile WFI to a concentration of 50 mg/mL resulting in a buffered, isotonic, preservative-free solution with a total extractable volume of 10 mL. Study drug will be prepared in a 250-mL IV bag of 0.9% saline. The equivalent volume of reconstituted NEOD001 will be withdrawn prior to transferring the drug solution into the IV bag, such that the total IV bag volume will be 250 mL.

Refer to the Pharmacy Manual for complete information on preparing and administering the study drug.

The study drug should only be administered in settings where emergency resuscitative equipment and personnel trained in the management of anaphylaxis are immediately available to treat systemic reactions under the direct supervision of a physician.

The study drug will be administered once every 28 (± 5) days at the infusion duration established in Study NEOD001-001 or over 60 (± 10) minutes. The length of the infusion may be extended over a longer period of time as clinically indicated.

NEOD001 contains no antimicrobial preservatives. Once reconstituted, storage of study drug, inclusive of dilution and administration, should be limited to 24 hours under refrigerated conditions or 4 hours at room temperature. If it is anticipated that the infusion will extend beyond 4 hours, the reconstituted study drug should be split into multiple bags to ensure that no amount of reconstituted study drug will be at room temperature for longer than 4 hours (i.e., from the time of reconstitution of the vial to end of the infusion of a bag). The additional bag(s) should remain refrigerated until ready for use. The volume contained in the administration tubing should be completely flushed using 30 mL of 0.9% Sodium Chloride Injection (USP) after administration of study drug. The infusion line should NOT be used for blood draws.

Postdose Monitoring Period: All subjects will be closely monitored after completion of the study drug infusion as follows:

- Subjects will be closely monitored for possible infusion-associated AEs and/or hypersensitivities for approximately 90 (± 10) minutes after completion of the study drug infusion to assess for possible infusion-associated AEs and/or hypersensitivities.
- Beginning with the third infusion, the Investigator may decrease the postdose monitoring time to no less than 60 minutes, if no infusion-related reactions were observed in the previous infusions and allowed per the IRB/IEC.

- The Investigator may increase the postdose monitoring time if deemed appropriate or per local standards. In the event of any clinical concerns or suspicious signs or symptoms after the infusion, the subject will remain under observation for as long as the Investigator deems it appropriate.

5.4 DOSE ADJUSTMENTS

5.4.1 Withholding of Study Drug

Subjects with symptomatic orthostatic hypotension or systolic BP <85 mmHg, which in the medical judgment of the Investigator would interfere with subject's ability to safely receive treatment, will have study drug withheld.

5.4.2 Management of Suspected Infusion-Related/Hypersensitivity Adverse Events

In the event of a suspected infusion-related and/or hypersensitivity AE, the infusion should be immediately discontinued and appropriate supportive therapy should be administered, which may include epinephrine, IV fluids, corticosteroids, vasopressors, oxygen, bronchodilators, antihistamines, or acetaminophen. Subjects should be evaluated and carefully monitored until there is complete resolution of the AE or hypersensitivity signs and symptoms. In addition to the institution's recommended assessments, blood samples should be obtained in the event of a suspected infusion-related and/or hypersensitivity AE for assessment of the following: tryptase, complements C3 and C4, serum NEOD001, and anti-NEOD001 antibody levels.

For subjects who have an infusion-related reaction, any subsequent infusion must be given with premedication. Within the 30-60 minutes before the start of each infusion, administer 25 mg diphenhydramine (or an equivalent H1 antihistamine) and 650 mg acetaminophen. All premedications will be recorded in the electronic case report forms (eCRFs).

For subjects with a Grade 2 infusion-related AE, if it is appropriate to restart the infusion, it should be done at 50% of the original rate (e.g., if the initial infusion is administered over 60 minutes, the new rate should be based on administering 250 mL over at least 90 minutes). If the subject is to receive additional infusions in subsequent weeks, the rate of these infusions should be discussed with and agreed upon prospectively by the Investigator and the Medical Monitor.

If a subject experiences a Grade 3 infusion-related and/or hypersensitivity AE, the infusion should not be restarted. The decision to continue dosing at the subject's next scheduled administration should be discussed with the Medical Monitor. If the decision is made to proceed with dosing, the dose will be reduced by 50%, in addition to a 50% reduction of the original infusion rate. Subjects who have an infusion-related and/or hypersensitivity AE at the subsequent scheduled study drug administration must have study drug permanently discontinued and have an EOS Visit per Section [6.1.3](#).

Subjects who experience a Grade 4 infusion-related and/or hypersensitivity AE must have study drug permanently discontinued and have an EOS Visit per Section [6.1.3](#).

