Due to the limited number of infusion-site related reactions reported to date, premedication of subjects prior to the start of NEOD001 infusion is not required in the NEOD001-OLE001, NEOD001-201, and NEOD001-OLE251 protocols. As of 30 September 2016, 221 subjects had been dosed in the 4 completed or ongoing studies. In Study NEOD001-CL002 (VITAL), 129 subjects received a total of 534 infusions of blinded study drug (24 mg/kg NEOD001 plus standard of care or placebo plus standard of care). In Study NEOD001-201 (PRONTO), 23 subjects received a total of 51 infusions of blinded study drug (24 mg/kg NEOD001 or placebo). In Study NEOD001-001, 69 subjects received 994 infusions of NEOD001 (up to doses of 24 mg/kg). In the completed Study NEOD001-001, 9 infusion-site reactions were reported (6 subjects) and most (n=7; 78%) were classified as Grade 1. As noted above, 1 subject in the ongoing Study NEOD001-201 experienced an event of vasovagal syncope (characterized by bradycardia, hypotension, and syncope). Another aspect of safety monitoring in studies of NEOD001 has been a required postinfusion observation time ranging from 60 to 120 minutes. In addition to this study, Studies NEOD001-201 and NEOD001-OLE251 allow for flexibility in monitoring time if no reactions are seen after the first 2 infusions, as described in Section 5.3.

Based on the data available to date, NEOD001 has been well tolerated as single-agent therapy in subjects with AL amyloidosis and no clinically significant safety signals have been identified. See the current NEOD001 Investigator's Brochure for detailed clinical information.

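### Protocol 5.4.2 asks for a Grade 2 restart at half the original rate, but its 60-minute example allows up to 67%; half rate needs 120 minutes, not 90

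*Protocol*

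**What the plan says.** Protocol 5.4.2 requires the infusion to be stopped at once when an infusion-related or hypersensitivity event is suspected. After a Grade 2 infusion-related event, "if it is appropriate to restart the infusion", the rule is that "it should be done at 50% of the original rate". An example in the same sentence takes an initial infusion of 60 minutes and says that "the new rate should be based on administering 250 mL over at least 90 minutes".

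Protocol 5.3 supplies the volume and the usual duration. The bag is made up "such that the total IV bag volume will be 250 mL", and the drug is given "at the infusion duration established in Study NEOD001-001 or over 60" (±10) minutes.

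The Grade 3 paragraph of 5.4.2 does not allow a restart. If dosing continues at the next scheduled visit, it halves both the dose and the infusion rate, and it gives no worked duration.

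**The concern.** At a fixed volume, halving the rate doubles the time. An example that lengthens 60 minutes to 90 therefore cannot illustrate a 50% rate. The figure of 90 is 1.5 × 60, so the author may have added 50% to the duration instead of taking 50% off the rate. The documents do not say so.

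The instruction is used at the bedside, on the day, for a subject who has just had a Grade 2 reaction. For later infusions, 5.4.2 requires the investigator and the Medical Monitor to agree the rate in advance. It states no such check for the same-day restart, so the site depends on this one sentence. It is also the section's only worked rate, and a site could carry the same conversion over to the 50% rate reduction after a Grade 3 event; that is an inference.

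**Working it through.** **Inputs**
- Volume: 250 mL (Protocol 5.3, and the example in 5.4.2).
- Original duration in the example: 60 minutes (5.4.2).
- Required restart rate: 50% of the original (5.4.2).
- Minimum time in the example: 90 minutes (5.4.2).

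**Rates** (rate = volume / time)
- Original: 250 / 60 = 4.167 mL/min.
- Half rate: 0.5 × 4.167 = 2.083 mL/min. Time for 250 mL: 250 / 2.083 = 120 minutes.
- Example floor: 250 / 90 = 2.778 mL/min.
- Floor against original: 2.778 / 4.167 = 0.667, a reduction of one third.
- Floor against half rate: 2.778 / 2.083 = 1.333; the difference is 0.694 mL/min.

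**Can 90 minutes be recovered as half rate?** I tried the readings that might produce it.

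| Reading | Result |
|---|---|
| Original infusion at the lower window limit, 50 min | Half rate takes 100 min; 90 min is 55.6% of the original rate |
| Original infusion at the upper window limit, 70 min | Half rate takes 140 min; 90 min is 77.8% of the original rate |
| 30 mL line flush added to both volumes | (280/90) / (280/60) = 66.7%, unchanged |
| 90 min as total pump time, first part at full rate | 30 + 60 = 90 only if exactly half the bag had already run; the text bases the rate on the whole 250 mL |
| Original duration for which 90 min is half rate | 45 min; the example says 60 |
| Duration lengthened by 50% | 60 × 1.5 = 90 min, which is two thirds of the rate |

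No reading that keeps the stated volume and the 60-minute original makes 90 minutes equal to half rate.

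**How often it could matter (illustration only).** For the parent study, Protocol 1.3.2 reports that "9 infusion-site reactions were reported (6 subjects) and most (n=7; 78%) were classified as Grade 1", among 994 infusions.
- Above Grade 1: 9 − 7 = 2 at most.
- Per infusion: 2 / 994 = 0.20%, exact 95% interval 0.02% to 0.73%.
- Ceiling on infusions here: (27 + 42) × 36 = 69 × 36 = 2,484.
- Expected events: about 5 (0.6 to 18).

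This projection assumes that those reactions are the events 5.4.2 has in mind, that the parent-study rate carries over although doses there ran from 0.5 to 24 mg/kg, that infusions are independent, and that all 69 subjects enrol and receive all 36 infusions. Nine reactions in six subjects means that some subjects reacted more than once, so independence is doubtful. The grades of the two events are not given, and a Grade 3 event could not be restarted. No restart probability is given either.

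**The case against.** The strongest reply is that the sentence has a compliant reading. The 50% is the rule; the 90 minutes is an example and a floor. A 120-minute restart meets both, and the Grade 3 paragraph's 50% rate reduction supports 50% as the intended figure. On that view this is a poor example under a clear rule.

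There are also safeguards. The infusion stops at once, supportive care is given, and the subject is monitored until the event has resolved. Restarting is discretionary, and later infusion rates after Grade 2 go to the Medical Monitor. All subjects had at least 9 months of prior treatment (Protocol 4.1), and a history of Grade 3 or higher infusion-associated events excludes (4.2). Protocol 5.3 also says "Refer to the Pharmacy Manual for complete information on preparing and administering the study drug"; that manual is not available here and may state the rate correctly. Finally, SAP section 11 records that the NEOD001 program was discontinued, which limits what a protocol edit can still change.

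Most of this stands as a limit on consequence. The projected event count is weak and the finding does not need it. But a floor does not repair the example: an illustration of a 50% rule should not admit 67%, and a site that programs 90 minutes has done what the example says. Nothing else in the protocol or SAP reconciles the two numbers.

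**Conclusion.** The point holds. For a 60-minute original infusion, the example permits a restart at up to 67% of the original rate where the rule requires 50% (2.78 against 2.08 mL/min, or 90 against 120 minutes for 250 mL). The arithmetic needs only the 250 mL volume and the 60-minute duration, both stated. The text does not prove which number is the slip, but 50% is the natural one to keep: it is the stated rule, it recurs for Grade 3, and the 90 minutes appears only as an example.

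The consequence is small in numbers and touches no endpoint. It still should be corrected, because it is a wrong figure in a patient-safety instruction. With the program discontinued, the correction also matters for judging past restarts against the right rule and for any reuse of the text.

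**What to change.** If 50% is intended, replace the 90 minutes with at least 120 minutes or, better, with at least twice the original infusion duration. The second form also covers infusions that did not run for 60 minutes. If the sponsor did mean 90 minutes, restate the rule as about 67% of the original rate, that is 1.5 times the original duration. Either way, make the Pharmacy Manual agree.

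The cost is one phrase and no new procedure. For a 60-minute infusion, the restart takes at most 30 minutes longer than the 90-minute floor. If a fraction f of the bag had run before the stop, total pump time for an original duration D is fD + 2D(1 − f) = 2D − fD, so at most 2D: 120 minutes for D = 60 and 140 minutes for D = 70.

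- **Storage.** Protocol 5.3 has reconstituted drug "limited to 24 hours under refrigerated conditions or 4 hours at room temperature". Of those 240 minutes at room temperature, 240 − 120 = 120 or 240 − 140 = 100 minutes remain for preparation and the pause. For much longer original infusions the limit could bind. Bag splitting in 5.3 is framed for a long infusion foreseen in advance, so it may not help after an unplanned stop. That constraint already follows from the 50% rule; correcting the example does not create it.
- **Reporting.** Pump time stays below the 2.5-hour (150-minute) prolongation category in SAP 9.2.6. If the SAP counts the pause as infusion time, a pause of more than 30 minutes (D = 60) or 10 minutes (D = 70) could cross it.
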